appropriateness however of the reduced dosing could not be assessed due to the lack of clinical information. Another clear limitation of this study is the lack of effectiveness data and information on adherence.

Norway has a relatively homogenous and stable population of just over 5 million and a publicly funded healthcare system. Health-related data is systematically captured in electronic format in several registers, including National Health Registers that contain data on hospitalizations, prescriptions as well as causes of death of all inhabitants. Hospital and primary care Electronic Medical Records (EMRs) information are also available. Inhabitants of Norway have a unique personal identification number (PIN) which is used to link information from the various health registers.

Extraction of large amounts of data from EMRs is often a limiting factor. An automated data extraction tool available in Scandinavia (Customised eXtraction Program [CXP], IQVIA) was shown to efficiently and reliably extract EMR data from hospitals and primary care clinics across the country in full adherence to the data protection rules(5). This unique methodology automatically extracts structured and unstructured EMR data for large numbers of patients and assigns identifiers that make cross-linking with registry data possible on an individual patient level, while ensuring patient anonymity. The methodology of the CXP tool was developed in Sweden and it has been applied in primary care in Norway. However it has not yet been applied with Norwegian hospital EMRs.

8. Research questions and objectives

This population-based study offers a unique opportunity to assess both the effectiveness and safety of NOACs (rivaroxaban, dabigatran, apixaban) compared to warfarin in OAC naïve NVAF patients in Norway. In addition, this study will serve as a pilot project to evaluate the operational feasibility as well as the usefulness of linking the EMR data to the Norwegian Health Registers.

8.1 Primary objective:

- To assess the incidence rates of:
 - a. ischemic stroke (effectiveness)
 - b. intracranial hemorrhage (safety)

in OAC naïve NVAF patients who are dispensed individual NOACs for the first time and compare with the corresponding rates in OAC naïve users of warfarin in a propensity score matched population.

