9.2 Setting

The study will be undertaken in Norway and will comprise all adult patients with NVAF who initiated treatment with either a NOAC or warfarin during the study period for the first time (OAC naïve first-time users). Study endpoints, discontinuation, switch to another OAC, death or end of study period will serve as censoring criteria.

The NVAF study population is defined in accordance with the 2018 European Heart Rhythm Association practical guide on the use of non-vitamin K antagonist oral anticoagulants in patients with atrial fibrillation, which define NOAC eligibility in NVAF patients as atrial fibrillation in the absence of rheumatic mitral stenosis or a mechanical heart valve.

Cohort 1 (registry study): Registries in Norway are nation-wide and provision of the information is mandatory, which eliminates the risk of both selection and re-call bias. The large and detailed dataset also makes it possible to adjust for other risk factors on which information is available.

In cohort 2, patients with NVAF diagnosis will be identified through extraction of patient-level data from EMRs from a number of hospitals in Norway, in order to describe these patients more closely regarding their clinical characteristics that are not available in nation-wide registers (e.g., in-patient treatments, anthropometric data and laboratory test results). This part of the

¹ Source: <http://www.legemiddelverket.no>

study is a pilot that will test the operational feasibility of accessing and linking the regional EMR data to the Norwegian Health Registers. Should the access to the regional EMR be granted, patients in cohort 2 will be identified and their EMRs extracted using the Pygargus Customized Extraction Platform (CXP). The extraction program has been used in a number of research projects since 2005 in the Swedish and Norwegian health care systems (6, 7). De-identified individual level data on age, gender, prescriptions, diagnoses, measures, laboratory tests, health care professional (HCP) visits, referrals, etc. can be collected from the EMRs into an encrypted database.

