9.2.2 Selection criteria

Depending on the data source, the following 2 cohorts will be recruited:

Inclusion criteria

Registry cohort (Cohort 1)

Cohort 1a:

- Age ≥ 18 at the date of first OAC dispensation (index date)
- Diagnosed with atrial fibrillation or flutter in the period 5-year pre-index period. Defined as ICD10 codes; I480 (paroxysmal AF), I481 (persisting AF), I482 (chronic AF), I483 (typical AF), I484 (atypical AF) or I489 (unspecified atrial fibrillation or flutter) as given by either NPR **or** as a OAC (warfarin, dabigatran, rivaroxaban or apixaban) dispensed on the reimbursement code for AF in NorPD (ICD10 I48 or ICPC-2 K78)
- Dispensation of a first-time prescription for an OAC during the study period 1 January 2014 to 31 May 2018. This initiation of an OAC is the index event and requires that there is no previous prescription for any OAC in the preceding 365 days (counted from the date of the first dispensation backward to the end of OAC supply).

Cohort 1b:

- Age ≥ 18 at the beginning of the study period (1 January 2014).
- Diagnosed with atrial fibrillation or flutter prior or during the study period. Defined as ICD10 codes; I480 (paroxysmal AF), I481 (persisting AF), I482 (chronic AF), I483 (typical AF), I484 (atypical AF) or I489 (unspecified atrial fibrillation or flutter) as given by NPR.
- No dispensation of a prescription for an OAC (warfarin, dabigatran, rivaroxaban or apixaban) during the study period 1 January 2014 to 30 June 2018. The index event will be the beginning of the study period (1 January 2014) and requires that there is no previous prescription for an OAC in the preceding 365 days.

EMR cohort (Cohort 2):

- Age ≥ 18 at the date of first OAC dispensation (index date).
- Diagnosed with atrial fibrillation or flutter in the 5-year pre-index period defined as one of the following ICD10 codes in the EMRs obtained from the hospitals in the South-

Eastern Health Region; I480 (paroxysmal AF), I481 (persisting AF), I482 (chronic AF), I483 (typical AF), I484 (atypical AF) or I489 (unspecified atrial fibrillation or flutter).

- Dispensation of a first-time prescription for an OAC (warfarin, dabigatran, rivaroxaban or apixaban) during the study period 1 January 2014 to 31 May 2018. This initiation of an OAC is the index event and requires that there is no previous prescription of any OAC in the preceding 365 days (counted from the date of the first dispensation backward to the end of OAC supply).

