Exclusion criteria (for both cohorts)

- Valvular atrial fibrillation defined as presence of ICD10 codes in NPR; I05.2 mitral stenosis with insufficiency, I05.8 other mitral valve diseases (mitral (valve) failure), I342 (non-rheumatic mitral valve stenosis), Z952 (presence of prosthetic heart valve) and procedure codes FKD (prosthetic replacement of mitral valve), FKA (Repair of mitral valve for stenosis), FKB (Annuloplasty of mitral valve for insufficiency), FKC (Repair of mitral valve for insufficiency), FKW (Other operations on mitral valve) and FMD (replacement of aortic valve).
- Deep Venous Thrombosis (DVT) as defined by ICD10 codes I80 (Phlebitis and thrombophlebitis), Pulmonary Embolism (PE) as defined by ICD10 code I26 or I82 (other venous embolism and thrombosis), Other venous embolism and thrombosis within last 6 months before index date.
- Knee and/or hip replacement surgery (NCSP procedure codes; NGB, NGC, NFB or NFC) 5 weeks before index date.

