9.7 Data analysis

All data analyses will be performed using SAS statistical software version 9.4., and will be reported in a manner consistent with the Strengthening the Reporting of Observational Studies in Epidemiology (STROBE) guidelines.

Descriptive statistics will be used to present the data where continuous variables will be summarized as mean, standard deviation, median, minimum and maximum. Categorical variables will be described by frequencies and related percentages. Summaries will be reported separately for the elderly +75 years (cohort 1 and 2) and patients with renal impairment (cohort 2). Annual frequency of different OAC treatment during the study period in addition to adherence to each NOACs (high, moderate, low, and poor) will be presented. Also a separate analysis will be done to characterize patients with NVAf who have not been treated with OAC.

In the following, cohort 1 (registry) and cohort 2 (EMR) will be analyzed separately, but using the same analytical approaches.

The analyses will be performed on the total sample as well as on a confounder adjusted sample. It has to be kept in mind that analyses based on the overall sample (non-confounder adjusted sample) is prone to bias (see section 9.9).

Three separate propensity score models will be conducted and a 1:1 matching will be performed for:

- warfarin vs apixaban
- warfarin vs dabigatran
- warfarin vs rivaroxaban.

No matching to compare the NOACs among each other (e.g. apixaban vs rivaroxaban) will be performed due to underlying differences in prescribing preferences of different NOACs.

The propensity scores (PS) will be based on demographic variables and clinically relevant medical history, e.g. cardiovascular risk factors, comorbidities and concomitant medications at baseline.

Patients who switch or discontinue the OAC treatment will be censored at the date of switch or discontinuation. It cannot be ruled out that the switch of OAC (censoring) could be informative, but it is handled as uninformative censoring in the analyses.

Detailed methodology for propensity score modeling, matching, handling of missing data, summary and statistical analyses in this study will be documented in a Statistical Analysis Plan (SAP), which will be dated, filed and maintained by the sponsor. The SAP may modify the plans outlined in the protocol; any major modifications of primary endpoint definitions or their analyses would be reflected in a protocol amendment.

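### The valvular-AF exclusion list has no code for rheumatic mitral stenosis without insufficiency, although Section 9.2 defines the study population by its absence

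*Protocol*

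**What the plan says.** Section 9.2 adopts a practice guide's criteria, which "define NOAC eligibility in NVAF patients as atrial fibrillation in the absence of rheumatic mitral stenosis or a mechanical heart valve". Two conditions therefore make a patient valvular: rheumatic mitral stenosis and a mechanical valve.

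Section 9.2.2 makes this operational for both cohorts. The mitral diagnosis codes are "I05.2 mitral stenosis with insufficiency, I05.8 other mitral valve diseases (mitral (valve) failure), I342 (non-rheumatic mitral valve stenosis". The prosthesis code is "Z952 (presence of prosthetic heart valve". The procedure codes are "FKA (Repair of mitral valve for stenosis", mitral replacement (FKD), annuloplasty and repair for insufficiency (FKB, FKC), a residual group of mitral operations (FKW) and aortic replacement (FMD).

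The inclusion criteria for cohort 1a carry no valve condition. A patient enters with an AF or flutter code in NPR, or "as a OAC (warfarin, dabigatran, rivaroxaban or apixaban) dispensed on the reimbursement code for AF in NorPD (ICD10 I48 or ICPC-2 K78".

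The primary objective (8.1) is to take event rates in new users of each NOAC and "compare with the corresponding rates in OAC naïve users of warfarin in a propensity score matched population". Section 9.7 bases the propensity score on "demographic variables and clinically relevant medical history, e.g. cardiovascular risk factors, comorbidities and concomitant medications at baseline". Table 4 in 9.3.1, which sets out the baseline variables, contains no mitral valve disease.

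**The concern.** The list names stenosis combined with insufficiency and stenosis of non-rheumatic origin, but not the plain rheumatic form, which is half of what 9.2 says the population must be free of. No reason is given, so it reads as an oversight.

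It matters because the patients who slip through would probably not be spread evenly over the treatment groups. If the protocol's eligibility statement reflects practice, a patient with rheumatic mitral stenosis who starts an anticoagulant would mostly start warfarin. Warfarin is the reference in all three matched comparisons. A subgroup found almost only in the reference arm, absent from the listed covariates and possibly at higher stroke risk, would raise the warfarin stroke rate and make every NOAC look better. A larger sample does not reduce an error of that kind.

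**Working it through.** **Step 1. The plan's own figures.** No number in the plan is in dispute, but the matched group sizes and null intervals give the scale. Section 9.5 gives about 70,000 patients, NOAC shares of 11%, 17% and 19%, and 90% matched:

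- dabigatran: 70,000 × 0.11 × 0.90 = 6,930
- apixaban: 70,000 × 0.17 × 0.90 = 10,710
- rivaroxaban: 70,000 × 0.19 × 0.90 = 11,970

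These match the plan. The exact (Clopper-Pearson) intervals at 2.43% stroke risk also reproduce: 2.08–2.81%, 2.14–2.74% and 2.16–2.72%. The intervals at a relative risk of 1.00 in Table 8 reproduce within 0.01; for dabigatran, 0.81–1.23 against the stated 0.81–1.24.

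**Step 2. Definition against code list.**

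| Condition | Position under 9.2 | Caught by 9.2.2? |
|---|---|---|
| Rheumatic mitral stenosis, no insufficiency, unoperated | excluded | no code |
| Mitral stenosis with insufficiency | excluded if rheumatic | yes, I05.2 |
| Mitral stenosis, operated | excluded if rheumatic | yes, FKA, FKD or FKW |
| Mechanical valve | excluded | yes, Z952, FKD, FMD |
| Non-rheumatic mitral stenosis | not named | yes, I342 |
| Mitral repair or annuloplasty for insufficiency | not named | yes, FKC, FKB |

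Only the first row is a condition that 9.2 excludes and the list fails to catch. I05.8 is glossed as other mitral disease (valve failure), so it does not cover that row by its label.

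**Step 3. Does anything else close the gap?** The inclusion criteria have no valve condition. Table 4 has no mitral covariate. The validation of NVAF against EMR data (8.3) is exploratory, uses cohort 2, and comes with no stated correction to cohort 1. The limitations in 9.9 do not mention the point.

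**Step 4. Illustrative size for ischemic stroke.** The documents give no frequency of the condition and no stroke risk for it, so both inputs are assumptions. Let f be the share of the matched warfarin arm with uncaptured rheumatic mitral stenosis and k their stroke risk relative to the other warfarin patients. Assume none in the NOAC arm, a true ratio of 1.00, and the plan's 2.43% for the other warfarin patients.

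Warfarin risk = 2.43% × [1 + f(k − 1)]

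Observed ratio = 1 / [1 + f(k − 1)]

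| f | Patients among 6,930 | k | Warfarin risk | Observed ratio |
|---|---|---|---|---|
| 0.5% | 35 | 2 | 2.442% | 0.995 |
| 0.5% | 35 | 3 | 2.454% | 0.990 |
| 1% | 69 | 2 | 2.454% | 0.990 |
| 1% | 69 | 3 | 2.479% | 0.980 |
| 3% | 208 | 2 | 2.503% | 0.971 |
| 3% | 208 | 3 | 2.576% | 0.943 |

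For example, 1 / (1 + 0.03 × 2) = 1 / 1.06 = 0.943.

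**The case against.** Several points on the other side are sound.

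- A reader might infer that the list leaves out rheumatic mitral stenosis altogether. It does not. I05.2 and the mitral procedure codes catch mixed and operated disease. What remains is isolated, unoperated stenosis never given a listed code. It is also only one of the two conditions in 9.2; the mechanical valve is covered.
- A reader might infer that the aortic replacement code and the mitral repair codes should be dropped because 9.2 does not name them. That does not follow. 9.2 names a mechanical valve without restricting its position, so FMD serves the definition, and removing it could readmit patients whom 9.2 excludes. Excluding mitral repair is stricter than 9.2 but applies to every treatment group, and nothing in the documents shows that it biases a comparison.
- A reader might infer that matching cannot deal with these patients. The documents do not go that far. Section 9.7 gives its propensity variables only as examples and leaves the model to the SAP, and 9.4 retrieves ICD-10 diagnoses from NPR. It can be said that no mitral covariate is listed. A covariate would in any case not make the cohort agree with 9.2.
- The concentration in warfarin is inferred from the eligibility statement; it is not documented.
- Even the largest illustrated shift, 0.943, lies inside every null interval in Table 8 (0.81–1.24, 0.84–1.19 and 0.85–1.17). That limits the practical weight, although a systematic shift is not excused by being narrower than the random error.

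The contradiction itself survives all of this. The code list is fixed in the protocol's selection criteria, whereas 9.7 hands to the SAP the modelling, matching, missing data and analyses.

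**Conclusion.** The point holds in a limited form. As written, 9.2.2 admits patients with isolated, unoperated rheumatic mitral stenosis, whom 9.2 excludes. They would be expected mainly on warfarin. If their ischemic stroke risk is higher, the stroke comparison is biased in favour of each NOAC.

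The size cannot be derived from the documents. For uncaptured shares of 0.5–3% and risks of 2–3 times, a true ratio of 1.00 would appear as about 0.995–0.94. This assumes that none of these patients are in the NOAC arms and that matching does not remove them. The effect is probably small unless the condition is common in the matched warfarin arm.

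A reader might extend the conclusion to the whole primary objective. The documents do not support that: they give no basis for a direction or a size for intracranial hemorrhage, the other primary outcome. The point should be fixed because the population would otherwise not match its own definition and the remedy is cheap, but it is not shown to undermine the primary results.

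**What to change.** Add the ICD-10 code for rheumatic mitral stenosis (I05.0) to the valvular-AF exclusion list in 9.2.2. The protocol does not print this code, so the sponsor should confirm it against the ICD-10 version used in NPR. Make the change before data extraction, because under 9.2.3 the dataset of NVAF patients is put together before it reaches the research group. Keep the valve replacement codes, which serve the mechanical-valve condition. A sentence saying that the mitral repair codes are deliberately stricter than 9.2 would help but is not essential.

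The cost is one added code and somewhat fewer warfarin patients. How many cannot be stated from the documents; counting those removed by the new code in each treatment group would settle both the number and the assumption that they are mainly on warfarin.

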9.2.3 Study population

Cohort 1 sampling:

The NorPD is a pseudonymized register which means that it is not possible to use dispensation of OAC as the starting point and as a source population. Being a pseudonymized register NorPD data needs to be the last register in the data collection that is linked to the other data sources. To circumvent this we will start with the Norwegian Census Register that will identify all Norwegian residents' of the age of 18 years and above during the study period. This dataset is sent to the NPR (for all patients with NVAF and without NVAF plus the relevant co-morbidities). Lastly, NorPD will identify all subjects with at least one OAC dispensation during the study period and link the registers (cohort 1a). A de-identified dataset with all NVAF patients having at least one OAC dispensed in the study period will be delivered to the research group (cohort 1a). Similarly, NorPD will identify all subjects that did not receive an OAC prescription during the study period and link the registers (cohort 1b). A de-identified dataset with all NVAF patients not having received an OAC prescription in the study period will be delivered to the research group (cohort 1b) for exploratory analysis.

[figure not shown]

Figure 2: Cohort 1 sampling procedure flow-chart

Cohort 2 sampling:

From the EMR extraction process all patients diagnosed with NVAf at selected hospitals in Norway between 2009 to the end of study will be selected. This cohort of patients will be linked with NPR and lastly NorPD will be added.

[figure not shown]

Figure 3: Cohort 2 sampling procedure flow-chart

9.2.4 Representativeness

The study captures the whole Norwegian population, ensuring representativeness for the country. Moreover, the Prescribed Drug Register is-almost complete. It keeps track of every single pill that is dispensed, in any pharmacy throughout the country, and this information is linked to the individual who received it. The quality of the Norwegian health registers is well known and they provide a unique source of information for post-marketing studies of drug use and outcomes.

9.3 Variables

9.3.1 Baseline characteristics

Table 4: Demography and clinical characteristics extracted for cohort 1 and 2

Variable	data source	Definition	Relevance
Age	FRG	Age in year	Co-variate and included in risk scores
Gender	FRG	Male or female	Co-variate and included in risk scores
Origin	FRG	Place of birth categorized as Norway, the Nordic countries, other Europe, rest of the world	Co-variate
Immigration date	FRG	Date of immigration out of Norway	Censoring
Emigration date	FRG	Date of emigration out of Norway	
Date of death	FRG	Date of death	Censoring and outcome variable
Alcoholism	NPR	ICD10 codes: E244, G312, G621, G721, I426, K860, O354, Z714, Z721, E52, K70, T51	Co-variate
Chronic kidney disease (CKD)	NPR	ICD10 code: N18 as an option 1 to define CKD Expanded list of codes to define CKD will be considered as an option 2, This list is being used for another ongoing study and is based on the approaches by Fleet et al (8)., Nielsen et al (9). and Weir et al (10). that in addition to identifying patients from the option 1 will allow an inclusion of patients with cystic kidney disease, unspecified kidney failure, chronic or unspecified nephritic syndrome, nephrotic syndrome, recurrent and	Co-variate

Variable	data source	Definition	Relevance
		persistent hematuria, nephropathy (diabetic, hypertensive, hereditary), chronic tubulo-interstitial nephritis, diabetes mellitus with kidney complications as having renal dysfunction (see Annex 3). The option 2 will be further clarified.	
End stage renal disease	NPR	ICD10 code: N185 or procedure codes KAGD40 (hemodialysis chronic) or KAS (renal transplant)	Co-variate Hemodialysis included in mHASBLED score
Congestive heart failure	NorPD	NorPD reimbursement codes for heart failure: I50 (ICD10) or K77 (ICPC) in ATC code group C	Co-variate. Included in CHA2DS2VASc score
Dementia	NPR	ICD10 codes F00-F04, G30	Co-variate
Diabetes	NorPD	ATC code A10A or A10B	Co-variate
Ischemic stroke	NPR	ICD10 codes: I63	Co-variate
Hemorrhagic stroke	NPR	ICD10: I60-62	Co-variate Included in mHAS-BLED score
TIA	NPR	ICD10 code: G45	Co-variate Included in CHA2DS2VASc score
Stroke&tia	NPR	ICD10: I60-I64	Co-variate Included in CHA2DS2VASc score
Thromboembolism	NPR	ICD10: I74	Co-variate

Variable	data source	Definition	Relevance
			Included in CHA2DS2VASc score
Hypertension	NorPD	Reimbursement codes in NorPD in ATC code group C: E10-E13, E15 (ICD10) or K86, K87 (ICPC)	Co-variate Included in mHASBLED and CHA2DS2VASc risk score
Peripheral artery disease	NPR	ICD10: I739	Co-variate Included in CHA2DS2VASc score
Ischemic heart disease	NPR	ICD10: I20-I25	Co-variate
Myocardial infarction	NPR	ICD10: I21-I22	Co-variate
Angina pectoris	NPR	ICD10: I20	Co-variate
Chronic obstructive pulmonary disease	NorPD	Reimbursement codes: J44 (ICD10) or R95 (ICPC) in ATC group R03	Co-variate
Cancer	NPR	ICD10 codes: C00 to C97	Co-variate Included in Charlson Co-morbidity score
Leukemia	NPR	ICD10 codes: C90-C96	Co-variate Included in Charlson Co-morbidity score
Lymphoma	NPR	ICD10 codes: C80 to C88	Co-variate Included in Charlson Co-morbidity score
AIDS	NPR	ICD10 codes B20 to B24	Co-variate

Variable	data source	Definition	Relevance
			Included in Charlson Co-morbidity score
Thrombocytopenia	NPR	ICD10 codes: D692, D693, D694, D695, D696, D698, D699	Co-variate
Anemia	NPR	ICD10 codes: D65-D67, D680, D681, D682, D683, D684, D685, D686, D688, D689, D50-D53, D55-D59, D60-D64	Co-variate
Hypo/hyperthyroidism	NPR	ICD10 code: E03 / E05	Co-variate
Systemic connective tissue disease	NPR	ICD10 codes: M30 to M36	Co-variate Included in Charlson Co-morbidity score
Peptic ulcer and bleeding	NPR	ICD10 codes: Ulcer K25 to K29. Gastrointestinal bleeding K920/K921/K922	Co-variate Included in Charlson Co-morbidity score
Chronic liver disease and impairment	NPR	ICD10 codes: K70-K77	Co-variate Included in mHASBLED score
Renal impairment	NPR	ICD10 codes: D63.8, E10.2, E11.2, E13.2, I12.0, I13.1, I13.2, N02.x, N03.x, N04.x, N05.x, N07.x, N08.x, N11.x, N14.x, N18.x, N19, Q61.x	Co-variate Used in stratified analyses
Surgery performed in the study period	NPR	All NCSP codes including codes for active surgery	Co-variate. Adjust or exclude for in bleeding outcomes
Imidazol and triazol derivates	NorPD	ATC codes J02AB and J02AC	Co-variate. Interaction

Variable	data source	Definition	Relevance
Low-dose aspirin	NorPD	ATC code: B01A C06	Co-variate Included in mHASBLED score
Immunosuppressive treatments	NorPD	ATC code: L04A	Co-variate
Anti-platelet treatment (non aspirin)	NorPD	ATC code: B01A	Co-variate Included in mHASBLED score
Non-steroidal anti-inflammatory drugs (NSAID)	NorPD	ATC code: M01A	Co-variate. Included in mHASBLED score
Acid secretory drugs	NorPD	ATC code: A02B	Co-variate
Heparin	NorPD	ATC code: B01AB	Co-variate
Anti-arrytmic drugs class iii	NorPD	ATC code C01BD	Co-variate. Interaction
Rifampicin	NorPD	ATC code J04AB	Co-variate. Interaction
Anti-hypertensives	NorPD	ATC code: C02	Co-variate
Diuretics	NorPD	ATC code: C03	Co-variate
Beta-blockers	NorPD	ATC-code: C07	Co-variate
Calcium antagonists	NorPD	ATC-code: C08	Co-variate
Renin-angiotensin system drugs	NorPD	ATC-code: C09	Co-variate

Variable	data source	Definition	Relevance
Lipid-modifying drugs	NorPD	ATC-code: C10	Co-variate
Reduced or standard dose NOAC at index	NorPC	Indicator variable whether on reduced (15 mg riva, 2,5 mg api, 110 mg dabi) or standard (20 mg riva, 5 mg api, 150mg dabi) at index dispensation	Co-variate
Prior OAC use	NorPD	Previous OAC use. OAC availability (time of exhaustion of last dispensation) in 365 days prior to index dispensation. From the time of exhaustion of last dispensation and initiation of OAC in study period (> 12 months pre-index)	Co-variate
Previous bleeding hospitalization	NPR	ICD codes listed in section 9.3.4.2	Co-variate Included in mHASBLED
Modified HAS-BLED score	NPR and NorPD	
 - Hypertension defined by dispensation of at least one anti-hypertensive drug (see definition for hypertension above) last year prior to index date. 1 point - Renal impairment as defined by either hemodialysis (procedure code KAGD40) or kidney transplantation (procedure code KAS) or CKD stage 3 and 4 (ICD10 code N183, N184, N185). Expanded list of codes to define CKD will be considered as an option 2, 1 point - Liver impairment (ICD10 K70-K77). 1 point - Stroke during the last year prior to index visit (see definition). 1 point - Prior major bleeding (critical organ) last year before index date (see definition in 9.3.4.2) 1 point 	Bleeding risk score used as co-variate and effect modifier

Variable	data source	Definition	Relevance
		
 - Age \geq 65 years. 1 point - Therapy with either Nonsteroidal Anti-inflammatory Drugs (NSAID M01A) or anti-platelets (B01AC) in the previous year before index date. 1 point - Alcoholism (as defined by ICD10 codes above). 1 point 
Total HAS-BLED score from 0 to 8
	
CHA ₂ DS ₂ VASc	NPR and NorPD	
 - Chronic Heart Failure by NorPD reimbursement codes for heart failure: I50 (ICD10) or K77 (ICPC). 1 point - Hypertension defined by dispensation of at least one anti-hypertensive drug last year prior to index date (see definition above). 1 point - Diabetes defined by dispensation of at least one anti-diabetes drug last year prior to index date (see definition above). 1 point - Age \geq75 years (2 points) or age 64-74 years (1 point) - Previous stroke, TIA or thromboembolism by ICD10 codes (see definition above). 2 points - Peripheral artery disease (ICD10; I739). 1 point - Gender (male=1 point, female=0 point) 
Total score 0 to 9
	Stroke risk score used as co-variate and effect modifier
Charlson co-morbidity index	NPR and NorPD	
 - Age: \leq41 years (0 point), 41-50 years (1 point), 51-60 years (2 points), 61-70 (3 points), \geq71 years (4 points) - Myocardial infarction. 1 point - Congestive Heart Failure. 1 point - Peripheral Vascular Disease. 1 point - TIA or stroke. 1 points - Dementia. 1 point 	Co-morbidity risk score and co-variate

Variable	data source	Definition	Relevance
		
 - COPD. 1 point - Connective Tissue Disease. 1 point - Peptic ulcer and bleeding 1 point - Diabetes. 1 point - Moderate to severe Chronic Kidney Disease (combined CKD and ESRD). 2 points - Leukemia. 2 points - Lymphoma. 2 points - Solid tumour. 2 points - Liver disease. 3 points - Solid tumour with metastasis. 6 points - AIDS. 6 points Total score from 0 to 37	

Table 5: Additional clinical characteristics to be retrieved for the EMR cohort (cohort 2)

Variable	Data source	Operation definition	Relevance
Height	EMR	Height in centimeters from time point closest to the index date	Co-variate
Weight	EMR	Weight in kilogram from time point closest to the index date	Co-variate
Smoking habits	EMR	Smoking habits retrieved as free text search. Converted to pack-years	Co-variate
Alcohol abuse	EMR	Alcohol abuse search as free text	Co-variate
International normalised ratio	EMR	Retrieve all INR measurements from index to the end of study. Calculated INR mean during the study period	Co-variate. Imputation
Blood haemoglobin	EMR	Retrieve all Hb measurements from index to the end of study. Calculated Hb mean during the study period. Identify episodes of more than 20 g/L fall in hemoglobin	Co-variate. Bleeding endpoint
S-Creatinine	EMR	Retrieve all s-creatinine measurement from index to the end of study. Calculate eGFR (ml/min) and categorise in CKD stages (1-5)	Co-variate
OAC dosing	EMR	Number of tablets used per days retrieved from dosing instructions. Especially important for warfarin dosing	Co-variate. Imputation and modelling of warfarin exposure in the registry cohort
Blood transfusions	EMR	Number of blood transfusion. More or equal to two transfusion units will be used in the ISTH bleeding definition	For ISTH bleeding outcome

Variable	Data source	Operation definition	Relevance
Fatal bleeding	EMR	Patients that die from bleeding while at hospital	For ISTH bleeding outcome

